7.1.5 COST EFFECTIVENESS ANALYSIS

The research team will assess the cost effectiveness of the overall Stroke Ready Program. Cost-effectiveness will be estimated for two intervention scenarios: Stroke Ready delivery and Stroke Ready development and delivery. This will inform the value of taking the Stroke Ready Intervention, “out of the box” and delivering it in a novel context and to separately assess the cost of developing and delivering a similar intervention in a novel context.

Cost inputs to the models will be carefully recorded throughout the project. For development costs, we will use budgets from the Stroke Ready pilot to estimate the cost of developing all materials used in this proposal — music video, workbooks, workshop content and print media. Delivery costs will be tracked with each phase of the Stroke Ready program. All Stroke Ready material expenditures (e.g. print media production, website maintenance, Facebook and Instagram content marketing boost) will be tracked, and as appropriate, assigned to either the hospital or community portion of the intervention. To track personnel time for the workshops, we will maintain a spreadsheet and update it after every Stroke Ready workshop with the number of individuals involved, including participants. Each hour spent on the grant will be mapped to costs by assigning appropriate job titles and then mapping hourly wages for that title to Bureau of Labor Statistics Survey wage survey data by profession.³⁰ By summing work time costs and material costs, we will be able to estimate the total costs of the overall intervention and the hospital and community interventions separately. We will then separately estimate total quality adjusted life years (QALYs) gained by the Stroke Ready program (and separately for the hospital and community interventions) by applying the primary outcome treatment effect size to the total hospitalized population (i.e. 2.2% increase in treatment rates * 500 strokes = 11 additional patients treated) and estimated QALY gain using published stroke cost effectiveness models.^{31, 32} Estimated hospital and community effect sizes will be obtained from our secondary analysis assessing intervention component efficacy. The age distribution of patients who receive treatment via the intervention will be obtained from the overall Flint stroke population. By using repeated bootstrap samples from this population and repeatedly running the model we will estimate 95% credible intervals on the QALY gain. We will then estimate the Incremental Cost Effectiveness Ratio (ICER) by dividing estimated costs / estimated QALY gain across all scenarios.

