7.1.1 ANALYSIS OF THE PRIMARY ENDPOINT(S)

The primary analysis will be an interrupted time series comparison of acute stroke treatment rates in the three Flint hospitals. The pre-intervention period will be defined using EMR data prior to the start of the roll out of the community intervention. All patients admitted with a primary diagnosis of ischemic stroke in both the pre-intervention and intervention periods will be included in the primary analysis. Note: process measures evaluating the Stroke Ready campaign (quadrant crossover or music video view IP address) will not be linked to any obtained PHI. Logistic regression will be used to estimate the overall intervention efficacy (indicator variable) in a model predicting receipt of acute stroke treatment (binary variable). If a temporal trend exists in the pre-intervention period, we will adjust for the month since the start of the pre-period as a fixed effect while accounting for clustering at the hospital level. To maximize statistical power, both interventions (hospital-HUM00112536 and all community quadrants-this current protocol) will be parameterized with a single variable. With this approach, statistical power for the primary analysis will be more than adequate. Using hospital administrative and Medicare data, we estimate that at least 480 strokes per year will occur at the 3 Flint hospitals for a total of at least 1,440 strokes in the pre period and 1,800 in the post-period, but to be conservative we are requesting data from 2010 to 2021 about 8000 patients with a stroke. Assuming a doubling in treatment rates (pre-intervention Medicare treatment rate 2.2%),³⁷ we will have over 90% power to detect this difference considering a two-sample binomial difference in proportions. This estimate is consistent with prior simulation work based on ARIMA analyses (effect size of 1.0 (pre-intervention monthly treatment rate = 2.2%, standard deviation = 2.1, predicted post-intervention treatment rate 4.3%, auto-correlation=0.3).³⁸

7.1.2 SECONDARY ANALYSES: REGIONAL COMPARISONS AND QUADRANT-BASED ANALYSES TO ENHANCE CAUSAL INFERENCE

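### The planned 95% interval on QALY gain names no step that carries in the sampling error of the treatment effect, and the stroke count should cover the same period as the costs

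*Combined protocol and SAP*

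**What the plan says.** Section 7.1.5 builds the QALY gain in three steps.

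- **Extra patients treated.** These come from the estimated effect, "by applying the primary outcome treatment effect size to the total hospitalized population", spelled out as "i.e. 2.2% increase in treatment rates * 500 strokes = 11 additional patients treated".
- **QALY gain per treated patient.** This comes from published stroke cost-effectiveness models, with ages supplied as follows: "The age distribution of patients who receive treatment via the intervention will be obtained from the overall Flint stroke population".
- **Interval.** "By using repeated bootstrap samples from this population and repeatedly running the model we will estimate 95% credible intervals on the QALY gain". It is described for QALY gain only; none is described for the ICER.

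On costs, the section says "Cost inputs to the models will be carefully recorded throughout the project" and "By summing work time costs and material costs, we will be able to estimate the total costs of the overall intervention"; one scenario adds development costs. The ICER is cost divided by QALY gain. Separate hospital and community QALYs are also promised, using effects from the component analysis. Section 7.1.3 puts the power of that analysis at 70% (community), 55% (hospital) and 21% (interaction), and calls it inadequate for hypothesis testing.

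On volume, section 7.1.1 expects "at least 480 strokes per year will occur at the 3 Flint hospitals". The synopsis gives two years of community delivery.

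**The concern.** QALY gain is a product: effect × strokes × QALY gain per treated patient. The resampling described acts on the third factor, through age. The first factor is an estimate from a before-and-after comparison of a rare outcome, and the section names no refit, standard error, draw or sensitivity range for it. If the analyst does what is written, the number of extra patients treated is the same in every replicate, and the 95% label covers case mix only.

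The analysis is meant to tell others what it is worth to deliver or develop the programme elsewhere. An interval without the effect's error would make that answer look firmer than the data allow. This is more serious for the component QALYs, whose effects the plan itself treats as exploratory.

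A smaller matter concerns time. The stroke count in the example looks like one year's volume, while the costs are totalled over a longer project. If both were used literally, cost and benefit would cover different periods.

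**Working it through.** **Inputs.** Pre-intervention rate 2.2%, doubling to 4.4%; 1,440 pre and 1,800 post strokes; at least 480 strokes per year (all section 7.1.1). 500 strokes and 11 extra treated (7.1.5). Two years of delivery (synopsis). Quadrant timetable (Table 1).

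**1. The plan's figures.** 0.022 × 500 = 11.0, as stated. Power for 2.2% v 4.4% with 1,440 and 1,800 strokes is 93.6% (two-sided 5% assumed, since none is stated), which agrees with the claim of over 90%.

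**2. Sampling error of the effect.**

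SE = √(0.022×0.978/1440 + 0.044×0.956/1800) = 0.00619, or 0.62 points.

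95% interval: 0.022 ± 1.96×0.00619 = 0.0099 to 0.0341.

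Per 500 strokes: 4.9 to 17.1 extra treated. Half-width 6.07/11 = 55%.

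**3. With a month term.** Section 7.1.1 adds one only if a pre-period trend exists. From the information matrix of a logistic model with a step and a linear month term, at 40 strokes per month (480/12):

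| Months pre/post | SE of log OR | 95% interval for OR 2.05 |
|---|---|---|
| 36/45 | 0.38 | 0.96 to 4.34 |
| 102/42 (assumed split of 2010-2021) | 0.29 | 1.15 to 3.63 |

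So with the term the interval reaches, or comes close to, no effect. Hospital clustering is not counted. If it and the trend together inflated the variance of the difference by an assumed factor of 2 or 4, the range per 500 would be 2.4 to 19.6 or −1.1 to 23.1.

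**4. How much the whole interval widens.** Let c be the between-patient SD of QALY gain divided by its mean, and N the number resampled; neither is given. The relative SE from case mix is c/√N, and from the effect 0.00619/0.022 = 0.281. Widening ≈ √((c/√N)² + 0.281²) / (c/√N).

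| c (assumed) | N = 11 | N = 500 |
|---|---|---|
| 0.3 | 3.3 | 21 |
| 0.5 | 2.1 | 12.6 |
| 1.0 | 1.4 | 6.4 |

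The interval widens in every cell, but by anything from 1.4-fold to 21-fold.

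**5. Time span.** 500/480 = 1.04 years of strokes. Two years: 960 × 0.022 = 21.1 extra treated, and 21.1/11 = 1.9.

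For the community component, Table 1 has the local intervention under way or completed in 4 + 3 + 2 + 1 = 10 of 16 quadrant-periods. With equal quadrant volumes, 960 × 10/16 = 600 strokes; 600 × 0.022 = 13.2; 13.2/11 = 1.2.

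**The case against.** **The effect is not declared fixed.** The section speaks of running the model repeatedly on resampled patients, and a team could refit the effect each time. That stands as a limit on wording: this is a step the plan leaves out, not an error it affirms. But nothing in the text says the effect is re-estimated, and the sentence before the bootstrap ties the resampled population to the age distribution.

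**The effect's error may not dominate.** A reader might infer that it is the main source of uncertainty and that the planned interval will be far too narrow. The documents do not support that. If only 11 patients were drawn and c were 1.0, case mix alone would give ±59%, similar to the ±55% from the effect. Uncertainty in the published models cannot be seen from here.

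**The 500 may be only an example.** It is never labelled annual, and the rule refers to the whole hospitalized population. So the documents do not show that the ICER will be inflated. The figure is, however, given as what the rule means, and no other period is stated, so a clarification is due.

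**A larger mismatch is tempting.** All 1,800 post-period strokes would give 1,800 × 0.022 = 39.6 extra treated, 3.6 times 11. But 1,800/480 = 3.75 years, and the documents do not tie the costs to that span; delivery lasts two. The 3.6 should not be used.

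**It is a supporting analysis.** True: the primary and secondary endpoints are untouched, and any mismatch in time would make the programme look less cost-effective, not more.

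**Conclusion.** The concern holds as a gap in the stated method. As written, the 95% interval on QALY gain reflects the age mix of Flint stroke patients and omits the sampling error of the treatment effect. That error alone is worth 4.9 to 17.1 extra treated per 500 strokes around the stated 11, assuming independent patients, no month term and the planned doubling. The real figure is likely to be wider. The direction is certain, but the overall widening cannot be stated without the bootstrap size and the QALY spread. The consequence is greatest for the hospital and community QALYs.

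The time-span point is secondary and conditional. If 500 is used literally against two years of cost, the overall-programme ICER is about 1.9 times too high; for the community component the factor is about 1.2, given equal quadrant volumes. Both factors take the cost period to be the two years of delivery.

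**What to change.** Amend section 7.1.5 so that each bootstrap replicate:

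1. resamples patients from the pre and post periods;
2. refits the effect model: the primary model for the overall effect, the component model for the hospital and community effects;
3. recomputes the extra patients treated;
4. draws the QALY gain per treated patient from the published model's uncertainty.

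Report percentile intervals for QALY gain and for the ICER. State the number of patients drawn and how hospital clustering is respected. A ratio is hard to read when the gain is near zero or negative, so also report the share of replicates with no gain.

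State one period, and count both strokes and costs over it. For the community component, count only strokes in quadrants already crossed over.

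The cost is SAP wording and more computation, on patient data the study already plans to obtain, and a wider reported interval.

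### As written, the planned ICER is a programme cost per QALY gained: its numerator omits the cost of the extra treatments and the later care they avoid

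*Combined protocol and SAP*

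**What the plan says.** Section 7.1.5 plans the analysis for two cases: "Cost-effectiveness will be estimated for two intervention scenarios: Stroke Ready delivery and Stroke Ready development and delivery". Its elements are as follows.

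- **Development cost** (second scenario only): "For development costs, we will use budgets from the Stroke Ready pilot to estimate the cost of developing all materials used in this proposal".
- **Materials**: programme expenditure, with the examples "print media production, website maintenance, Facebook and Instagram content marketing boost".
- **Labour**: "Each hour spent on the grant will be mapped to costs by assigning appropriate job titles", valued at published wages. The workshop log is to be kept "with the number of individuals involved, including participants", but no rule says whether participants' time is valued.
- **Total cost**: "By summing work time costs and material costs, we will be able to estimate the total costs of the overall intervention", and likewise for the hospital and community parts separately.
- **QALYs**: the treatment effect is applied to the hospitalised stroke population (the example is a 2.2% increase on 500 strokes, or 11 more treated patients) and combined with "estimated QALY gain using published stroke cost effectiveness models".
- **Ratio**: "We will then estimate the Incremental Cost Effectiveness Ratio (ICER) by dividing estimated costs / estimated QALY gain across all scenarios".

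The interval described is on the QALY gain. The section names no perspective, time horizon or discount rate.

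**The concern.** The programme produces QALYs only by causing more patients to receive tPA or endovascular treatment. Those treatments cost money and, if they reduce disability, avoid later care costs. Both belong to the same increment as the QALYs. The plan counts the health consequence of the extra treatments but not their financial consequences, so numerator and denominator do not describe the same comparison.

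What is at stake is how the figure can be used. A ratio called an ICER will be read against other ICERs, and this one would not be comparable. Section 2.1 also presents the programme as one that may reduce the expense of stroke, yet the planned ratio cannot show any such reduction. Costs and QALYs are further to be reported separately for the hospital and community parts. If the two parts change the mix of IV and endovascular treatment differently, the missing term differs between them and the comparison of their ratios is affected.

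**Working it through.** **The plan's own figure.** 0.022 × 500 = 11 extra treated patients, as stated. The plan gives no programme cost, QALY gain, treatment cost or ICER, so there is no ratio to reproduce.

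**Notation.** P = programme cost; n = extra treated patients; q = QALYs gained per extra treated patient; c = cost of acute treatment per extra treated patient; s = later care cost avoided per extra treated patient; d = c − s. Only n can be taken from the documents.

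**Formulas.**

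- Ratio as planned: P / (n q).
- Ratio with health-care costs: (P + n d) / (n q) = P / (n q) + d / q.
- Difference: d / q. P and n both drop out. With n = 39.6 (0.022 × the 1,800 post-period strokes in section 7.1.1) in place of 11, the shift would be the same.

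The two ratios agree only if d = 0, that is, if treatment cost and later savings cancel exactly.

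**Illustration (all dollar and QALY values assumed).** Shift d / q in USD per QALY:

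| d | q = 0.3 | q = 0.5 | q = 1.0 |
|---|---|---|---|
| +20,000 | +66,667 | +40,000 | +20,000 |
| +10,000 | +33,333 | +20,000 | +10,000 |
| 0 | 0 | 0 | 0 |
| −15,000 | −50,000 | −30,000 | −15,000 |

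With P = USD 250,000, n = 11 and q = 0.5, so that n q = 5.5:

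- as planned: 250,000 / 5.5 = USD 45,455;
- c = 20,000, s = 0: (250,000 + 220,000) / 5.5 = USD 85,455;
- c = 10,000, s = 25,000: (250,000 − 165,000) / 5.5 = USD 15,455.

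With P = USD 1,000,000 the three figures are USD 181,818, 221,818 and 151,818. The absolute shifts are unchanged, but the first is now 220,000 / 1,000,000 = 22% of the planned ratio instead of 220,000 / 250,000 = 88%.

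**What the omission leaves alone.** For a given effect size, the two scenarios share n, d and q. The difference between their ratios is development cost / (n q), which does not involve d. The level of each ratio is affected; the gap between the scenarios is not.

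**The case against.** The strongest defence has three parts.

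1. *Silence is not exclusion.* The listed costs are those that must be recorded as the project runs. Literature costs need no tracking, and the QALYs come from published cost-effectiveness models that could also supply costs. This would carry weight if the plan stopped at the list. It goes on to define total cost as labour plus materials and then divides costs by QALYs. From the published models it takes only the QALY gain. An analyst who follows the text would leave the other costs out.

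2. *A programme-budget view is legitimate.* Section 7.1.5 aims to inform sites that might adopt or develop such a programme, and for them programme cost per QALY is useful. The plan names no perspective, no willingness-to-pay threshold and no external ICER for comparison. All of that stands. It justifies reporting the ratio, but not calling it an ICER.

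3. *Size is unproven.* This also stands. The dollar values above are assumptions, and zero shift lies inside their range.

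A reader might infer that the plan flatters the programme because treatment costs are left out. The documents do not support that: avoided care costs are left out too, and they act in the opposite direction. A reader might also infer that the models already cited would supply the missing cost as a single extra input. By title, reference 31 concerns transfers after intracerebral haemorrhage and reference 32 concerns intra-arterial treatment added to IV tPA. Neither title indicates a model of IV tPA against no treatment.

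**Conclusion.** The point holds as a fault in the stated formula. Followed as written, section 7.1.5 yields programme cost per QALY gained, which differs from a payer or societal ICER by d / q. That result is algebraic and needs no assumption about programme cost or number treated. Direction and size cannot be determined from the documents, because neither d nor q is given.

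The consequence is confined to the economic analysis. Cost-effectiveness is not among the endpoints in the synopsis or the outcomes in Table 2, and no hypothesis test or sample size depends on it. The change should be made, but it does not bear on the validity of the primary analysis.

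**What to change.** Amend section 7.1.5 as follows.

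1. State the perspective, with the time horizon and discount rate that go with it.
2. Define incremental cost as programme cost plus, for each treatment type, extra treated patients times net lifetime health-care cost per treated patient: [P + n_IV d_IV + n_EVT d_EVT] / [n_IV q_IV + n_EVT q_EVT]. For each type, take cost and QALY inputs from the same published model.
3. Use the secondary IV-only effect to split the extra treated patients. Say how patients who receive both treatments are assigned, since section 6.2 counts the combination in the primary outcome.
4. Confirm that a model covering IV tPA against no treatment is available, and name it.
5. Report uncertainty on the ICER as well as on the QALY gain.
6. Report the present ratio separately, labelled *programme cost per QALY gained*. If nothing else is changed, make this relabelling.

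The cost is revised wording, at least two additional literature inputs, a split effect estimate in place of the single combined one, and a wider uncertainty interval. No new patient data are needed.

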7.1.6 SUSTAINABILITY

Project sustainability will come through several mechanisms: 1) training of peer leaders who will have knowledge of stroke warning signs and the importance of calling 911; 2) a complete community intervention package that can be administered with little to no training; 3) a well-positioned CAB to promote sustainability; and 4) optimized acute stroke care in a safety net hospital. The products of this application include a strategy to improve acute stroke treatments in safety-net hospitals and an easy to deliver Stroke Ready community intervention to allow for successful dissemination. If successful, this proposal will directly benefit the Flint community by increasing acute stroke treatment rates thereby decreasing post-stroke disability. Furthermore, it will inform future acute stroke interventions, especially in underserved, predominately African American communities.

8 DATA CONSIDERATIONS

8.1 DATA

Data and information collection from workshop participants will cease pending the approval of the IRB Amendment (Ame00084323). Previously collected satisfaction surveys and address forms (June 2018-January 2019) will be stored securely and analyzed. Pending amendment approval, there will be no data or information collected from workshop participants (no satisfaction surveys or address forms).

The only PHI identifiable data in this study will be addresses and hospital dates of stroke patients collected from the three Flint area hospital detailed below.

De-Identified

The community surveys, Speak to Your Health and the Flint Area Study, are publically available and de-identified. The Michigan State Inpatient Database (SID), which collects data on all acute care hospitalizations in the state of Michigan within a given year is also de-identified. The satisfaction survey and fidelity assessments will not include personal identifiers.

Identified

A process measure is the number of views of the Stroke Ready music video. This will be assessed by the number of internet hits from the Flint community via internet protocol (IP) addresses. The only use of this data is to assess the whether or not the video was viewed by and for the community it was intended. Additionally, basic analytics will be used to assess website visits. Data extracted will be number of views on the Stroke Ready website—total visits and visits from the Flint community via IP addresses. Exploratory analytics may include new versus returning users, frequency and engagement of site visits. We request a waiver of informed consent.

Hospital data will be obtained from the Flint area hospitals. Data may include basic demographics, treatments, date of admission and date of treatment, stroke process measures, comorbidities, and outcomes of stroke patients. This data will include identifiable information in the form of addresses, in order to map the stroke event, as well as dates. We expect some of this data to come from the EMR, billing records and Get With the Guidelines Stroke. We are working with each hospital to establish a data use agreement. We request a HIPAA authorization waiver and a waiver of informed consent.

All PHI data will be stored on the secure and UMHS approved cloud storage, M-Box. The data from the hospitals will be directly uploaded into M-Box. The only researchers with access to the identifiable PHI in M-Box will be Drs. [name], [name], [name] and [name]. A de-identified dataset will be created from the identifiable data and the only researcher with access to this PHI link will be Drs. [name], [name], [name] and [name]. After developing de-identified datasets, limited analytic datasets will be used for analysis.

For all identifiable data collected, the research team will not use them to personally identify a Stroke Ready workshop participant, stroke patient, or Stroke Ready video viewer.

